For the comparison of 150 mg PF-06823859 and placebo, assuming a SD of 8 and assuming a pooled sample size of approximately 10 and 11 completers respectively across the two Stages, we expect the half length of the 90% CI to be 5.75. For the comparison of 600 mg PF-06823859 and placebo, assuming a SD of 8 and assuming a pooled sample size of approximately 21 and 11 completers respectively across the two Stages, we expect the half length of the 90% CI to be 4.90.

No p-values will be presented for the comparisons listed in the objectives and endpoints of Section 2.2 for Stage 2.

9.1.3. Sample Size Determination in Stage 3

The major efficacy endpoint of interest in Stage 3 is the TIS,³¹ which is a continuous measure ranging from 0 to 100. The treatment effect is defined as the difference in mean TIS between the active and placebo treatment groups at Week 12. The standard deviation in TIS at Week 12 is estimated to be between 15 and 25 units.^{32,33}

The DM muscle disease cohort will enroll between 8 and 16 participants randomized 1:1 to active and placebo. Table 3 shows the estimated half widths of the 90% confidence intervals for the difference in mean TIS between the PF-06823859 600 mg arm and the placebo arm at Week 12 across a range of standard deviations and number of completers. For example, if 10 participants (5 active, 5 placebo) complete the Week 12 assessment and the SD of the TIS is 20, the estimated half width of the 90% confidence interval is approximately 20.8.

No p-values will be presented for the comparisons listed in the objectives and endpoints of Section 2.4 for the DM muscle cohort.

Table 3.	Estimated Half-widths of 90% Confidence Intervals for the Difference in
	TIS between Active and Placebo at Week 12

Number of completers (active: placebo)	Assumed SD of TIS	Half width of 90% CI
	15	17.4
8 (4:4)	20	23.3
	25	29.1
	15	15.6
10 (5:5)	20	20.8
	25	26.0
	15	14.2
12 (6:6)	20	19.0
	25	23.7
	15	13.2
14 (7:7)	20	17.6
	25	22.0
	15	12.3
16 (8:8)	20	16.4
	25	20.6

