9.2.2. Analysis of Secondary Endpoints

9.2.2.1. Analysis of the Secondary Endpoints in Stage 1

The values of CDASI activity and damage scores at each visit will be summarized by descriptive statistics. The estimates for treatment effect will be obtained by LANCOVA and ANCOVA methods described in Section 9.2.1 where the change from baseline of a corresponding score (ie, activity or damage score) will be used as a dependent variable. The ANCOVA analysis will be used as supportive analysis. Estimates and the confidence intervals for treatment effect will be presented for each of these methods.

9.2.2.2. Analysis of the Secondary Endpoints in Stage 2

The analyses and summaries of the secondary endpoints in Stage 2 will be the same as those in Section 9.2.2.1 except that they will be conducted for the data across the two Stages. No p-values will be presented for these analyses.

As a supportive analysis, summaries will also be presented for change from baseline in CDASI activity score after 12 weeks of active treatment, which includes pooled data from participants who received active treatment from Day 1 to Week 12 (CDASI measured at Week 12) and participants who received active treatment from Week 12 to Week 24 (CDASI measured at Week 24). This may be compared to the participants receiving placebo during the first 12 weeks. Baseline is defined as Day 1 for participants who received active treatment from Day 1 to Week 12 for participants who received active treatment from Day 1 to Week 12. Baseline is defined as Week 12 for participants who received active treatment from Week 12 to Week 12 to Week 12 to Week 24. Further details will be provided in the SAP.

9.2.2.3. Analysis of the Secondary Endpoints in Stage 3

The TIS at baseline is 0 indicating no change. The TIS at post baseline visits is scored as relative change from baseline. The absolute value of the TIS at each post baseline visit will be summarized by descriptive statistics. The estimates of the treatment effect from Baseline to Week 12 will be obtained by LANCOVA where the TIS will be used as a dependent variable. The model will include treatment (active dose and placebo), week and treatment by week interaction as fixed effects. An unstructured variance-covariance matrix will be allowed.

Estimates and the 90% confidence intervals for treatment effect will be presented. No p-values will be presented for these analyses.

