5.2.1. Analyses for Continuous Longitudinal Data

5.2.1.1. Longitudinal Analysis of Covariance (LANCOVA) Model

A discussion of this model may be found in Lu (2010). We will use the following variations of the method: LANCOVA-P and LANCOVA-S where letters P and S denote the versions that are used for primary (P) and sensitivity (S) analyses.

The LANCOVA-P model uses the change from baseline as an outcome and the baseline value as a covariate. The model assumes visit-independent adjustment of the mean outcome for baseline, saturated treatment by time model for the mean and an un-structured within subject error covariance matrix. Treatment and time are considered as factor variables and treatment by time is considered as unstructured interaction effect.

The LANCOVA-S model also uses the change from baseline as an outcome and the baseline value as a covariate. The model assumes a saturated baseline by time and treatment by time fixed effects and an un-structured within subject error covariance. Treatment and time are considered as factor variables and baseline by time and treatment by time are considered as unstructured interaction effects. This allows the baseline and treatment effects to vary over time.

Variations of LANCOVA-P and LANCOVA-S models with the covariance matrices that have less general structure (eg, compound symmetry) may be considered if there are convergence issues with the primary versions of the model.

The analysis will provide an estimate and a two-sided 90% confidence interval for the difference (for each of the active doses against placebo) in the expected values of the outcome at multiple visits.

The sample SAS code for the LANCOVA calculations is presented in Section 9.6.

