- For the CCl each of the three questions will be summarized by a single score (see Section 9.4.7).
- For the EQ-5D-5L, the summed number of checked boxes under each of the five sections will be reported (see Section 9.4.8).
- For the HAQ-DI, a single averaged score summarizes each of the corresponding patient-reported outcomes under the eight sections (see Section 9.4.6). In sections of the HAQ-DI relating to aids or devices or help from another person, each checkable box will be treated as binary data and summarized with proportions and frequency counts. A single score summarizes the severity of pain VAS.

6.3. Analyses and Summaries During Stage 3

6.3.1. Primary Endpoint in Stage 3

The primary endpoint in Stage 3 includes the incidence of adverse events (AEs) laboratory abnormalities, changes in vital signs, and electrocardiogram (ECG) findings. All safety summaries and analyses will be performed as specified in Section 6.7.

6.3.2. Secondary Endpoint(s) in Stage 3

6.3.2.1. Total Improvement Score in Stage 3

- Analysis population: FAS3.
- Analysis time points: Week 12 and intermediate scheduled time points.
- Analysis methodology: The TIS at post baseline visits are scored relative to baseline and the TIS at baseline is 0 by definition; thus all analyses are performed directly on the TIS. The estimates of the treatment effect from baseline to Week 12 will be obtained by MMRM where the TIS will be used as a dependent variable. This model uses fixed effects for treatment, time (visit), treatment by time, and a random effect for subject, Due to the unknown nature of the longitudinal data, different covariance

structures among repeated measures will be examined based on model diagnostics starting with the unstructured variance-covariance model.

- Supporting objective: Secondary objective.
- Reporting results: The absolute value of the TIS at each post baseline visit will be summarized by the following descriptive statistics:
 - The sample size, mean, standard deviation, median, minimum and maximum will be presented for each treatment arm (active and placebo).
 - The LS means, 90% confidence interval for the LS means, difference between the LS means of treatment groups (active treatment arm placebo) and the corresponding 90% confidence interval for the estimate. Plots of this data will also be presented. No p-values will be computed for the analysis in this stage.

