9.6. Examples of SAS Code for the LANCOVA and ANCOVA Analyses

Create data set ds where for each subject and each visit the following information is stored in the row of the data set.

Table 7. Input Parameters for LANCOVA and ANCOVA Analyses

Id	Subject's id
Cfb	Change from baseline
Time	time of interest (treated as a class variable). Only the post-baseline visits are included
Trt	Treatment group (stored as a class variable, trt="Active" denotes active treatment and "Control" denotes control treatment)
Base	Baseline observation of the outcome

The analysis will be implemented as follows. In all of the LANCOVA and ANCOVA analyses we use the reference baseline value XXX (see below) which is the mean of the baseline values for all participants.

%let basemean=XXX;

LANCOVA-P

The resulting estimates of the visit-dependent difference in means of cfb (active-control treatments) and means of cfb for active and control groups are stored in the dlancovaP and dlancovaMP data sets.

LANCOVA-S

The only difference between the LANCOVA-S and LANCOVA-P analyses is the addition of the time*base term to the model.

The resulting estimates of the visit-dependent difference in means of cfb (active-control treatments) and means of cfb for active and control groups are stored in the dlancovaS and dlancovaMS data sets.

ANCOVA

Create data set ds as described in the Table 7 and sort it by visit. The analysis will be implemented as follows

```
proc mixed data=ds;
by visit;
class id trt (ref="Control") visit;
model cbaseline = trt baseline /ddfm=kr;
lsmeans trt / at baseline = &basemean alpha=0.10 cl pdiff;
ods output diffs= dancovaS lsmeans= dancovaMS;
run;
```

The resulting estimates of the visit-dependent difference in means of cfb (active-control treatments) and means of cfb for active and control groups are stored in the dancovaS and dancovaMS data sets.

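### Stage 3 precision table uses the normal quantile, so its 90% half-widths are too narrow: 18% (4:4) to 7% (8:8) on t with 2n-2 df, or 13% to 5% as expected widths

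*Protocol*

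**What the plan says.** Protocol Section 9.1.3 defines the quantity of interest: "The treatment effect is defined as the difference in mean TIS between the active and placebo treatment groups at Week 12". It plans 8 to 16 participants randomised 1:1 and takes the SD of TIS at Week 12 to lie between 15 and 25. It then says that "Table 3 shows the estimated half widths of the 90% confidence intervals for the difference in mean TIS", for 4:4 to 8:8 completers. In the worked example (5:5, SD 20), "the estimated half width of the 90% confidence interval is approximately 20.8". The section names no quantile and does not say that the SD is treated as known.

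The planned analysis estimates the variance. Protocol Section 9.2.2.3 fits TIS with treatment, "week and treatment by week interaction as fixed effects. An unstructured variance-covariance matrix will be allowed". There is no baseline covariate, because TIS is 0 at baseline by definition. SAP Section 6.3.2.1 has the same fixed effects, and says of the covariance that different "structures among repeated measures will be examined based on model diagnostics starting with the unstructured variance-covariance model".

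No degrees-of-freedom method is stated for the TIS model. The only model code readable in SAP Section 9.6 is for the ANCOVA: "model cbaseline = trt baseline /ddfm=kr", which requests Kenward-Roger degrees of freedom and hence t-based limits.

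**The concern.** A half-width computed with 1.645 is what one would report if the SD were known. With 4 to 8 completers per arm it is not known, and the t quantile on so few degrees of freedom is clearly larger. The discrepancy runs one way: every entry is too narrow, and the shortfall is greatest at the smallest cohort sizes the protocol allows.

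Stage 3 efficacy is secondary to safety, no hypothesis is tested and no p-values are given. The 90% interval is therefore the main inferential output for TIS, and Table 3 is the only precision figure offered for this cohort. A reader deciding whether 8, 10 or 16 participants can say anything useful about TIS would take that precision from this table.

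**Working it through.** **Inputs.** Two-sided 90% interval, so z = 1.645; SD 15, 20, 25; n = 4 to 8 completers per arm (all from Protocol Section 9.1.3).

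**Step 1: reproduce the printed table.** Half-width = z × SD × √(2/n). For 5:5 and SD 20: 1.645 × 20 × √0.4 = 20.81, printed 20.8. For 4:4 and SD 25: 1.645 × 25 × √0.5 = 29.08, printed 29.1. All 15 cells agree within 0.05. Neither t-based version below reproduces any cell, so the normal quantile is what was used.

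**Step 2: degrees of freedom under the planned model.** With complete data, treatment, week and their interaction with an unstructured covariance and no baseline covariate give a Week 12 contrast equal to the two-group comparison on 2n-2 df. Nothing in the model narrows it by baseline adjustment.

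**Step 3: t quantile, observed SD equal to the assumed SD.** Half-width = t(0.95; 2n-2) × SD × √(2/n).

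**Step 4: expected half-width.** Multiply Step 3 by E[s]/SD = √(2/ν) × Γ((ν+1)/2)/Γ(ν/2), with ν = 2n-2. This factor is 0.959, 0.969, 0.975, 0.979 and 0.982 for the five rows.

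| Completers | df | t | Printed, SD 15/20/25 | t-based, SD 15/20/25 | Excess | Expected, SD 20 | Excess |
|---|---|---|---|---|---|---|---|
| 4:4 | 6 | 1.943 | 17.4/23.3/29.1 | 20.6/27.5/34.4 | 18% | 26.4 | 13% |
| 5:5 | 8 | 1.860 | 15.6/20.8/26.0 | 17.6/23.5/29.4 | 13% | 22.8 | 10% |
| 6:6 | 10 | 1.812 | 14.2/19.0/23.7 | 15.7/20.9/26.2 | 10% | 20.4 | 7% |
| 7:7 | 12 | 1.782 | 13.2/17.6/22.0 | 14.3/19.1/23.8 | 8% | 18.7 | 6% |
| 8:8 | 14 | 1.761 | 12.3/16.4/20.6 | 13.2/17.6/22.0 | 7% | 17.3 | 5% |

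The t-based row for 8:8 equals the printed row for 7:7. Solving for the sample size at which the t-based half-width equals the printed one gives 2.0 to 2.2 more completers in total than each row lists. On expected half-widths it is 1.5 to 1.7 more.

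**Step 5: a simpler covariance structure.** The Stage 3 Schedule of Activities has no Week 1 MMT-8, so TIS exists up to Week 12 only at Weeks 4, 8 and 12. Under compound symmetry over three visits with within-subject correlation r, the Satterthwaite df are (2n-2) × 9 / [(1+2r)² + 2(1-r)²]. The documents give no r, so 0.3, 0.5 and 0.7 are assumed.

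| Completers | df at r = 0.3/0.5/0.7 | Excess, t-based | Excess, expected width |
|---|---|---|---|
| 4:4 | 15.3/12.0/9.1 | 6.5/8.4/11.3% | 4.7/6.1/8.3% |
| 8:8 | 35.6/28.0/21.2 | 2.7/3.4/4.6% | 2.0/2.5/3.3% |

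Even at r = 0 the t-based excess is 5.4% at 4:4 and 2.3% at 8:8.

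**Stage 2, for comparison.** Section 9.1.2 uses the same quantile: for 10 and 11 completers, "we expect the half length of the 90% CI to be 5.75", and 8 × √(1/10 + 1/11) × 1.645 = 5.75. For 21 and 11 it prints 4.90. Unadjusted t gives 6.04 (19 df) and 5.05 (30 df). That model does adjust, however (SAP Section 5.2.1.1: "The LANCOVA-P model uses the change from baseline as an outcome and the baseline value as a covariate"). An assumed baseline correlation of 0.3, with one df spent on baseline, gives 5.78 and 4.83. No error is shown there.

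**The case against.** The strongest reply is that the sums are right for their formula. The protocol describes the entries as estimated, calls the example approximate and labels the SD as assumed, which reads as a conventional known-SD planning calculation. The practical weight is also small. Stage 3's primary endpoint is safety, the sample size is a range not derived from a precision target, and Table 3 already runs from 12.3 to 29.1. Within a row the SD range alone moves the half-width by 67% (25/15), and going from 8:8 to 4:4 moves it by 41% (√2). The 18% to 7% figure assumes the observed SD equals the assumed SD, and the average interval is only 13% to 5% wider. Finally, 2n-2 df is an inference, since the SAP may settle on another covariance structure and states no df method for TIS.

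Much of this stands as a limit on consequence. It does not rescue the table. Words such as estimated and approximately do not disclose a known-SD assumption, and the SD range covers uncertainty about the SD, not the choice of quantile. The covariance choice changes the size of the gap (roughly 2% to 11% under compound symmetry for the correlations tried) but not its direction. The uncertainty over df is a reason to state the df, not to keep the normal quantile. The Stage 2 figures are best treated as a documentation point only.

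**Conclusion.** The concern holds. Table 3 and its worked example use a normal quantile that the design and planned model do not support at 4 to 8 completers per arm. The printed half-widths should be 18%, 13%, 10%, 8% and 7% wider from 4:4 to 8:8 on t with 2n-2 df, or 13% to 5% wider as expected half-widths. This rests on complete data, an unstructured covariance and t-based limits. The last is a fair inference from the ANCOVA code but is not stated for TIS. The use of 1.645 is inferred from reproduction of all 15 cells and is not in doubt. The exact df could be higher under a simpler structure, which narrows the gap without removing it. The effect is confined to an overstated precision statement: no test, decision rule or required half-width depends on it.

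**What to change.** Recompute the 15 entries of Table 3 and the worked example in Protocol Section 9.1.3 with t quantiles. State the degrees of freedom and whether the entries take the observed SD as equal to the assumed one (5:5, SD 20: 23.5) or are expected half-widths (22.8). Either convention is acceptable if named. State the degrees-of-freedom method for the TIS model in SAP Section 6.3.2.1.

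Optionally, say in Section 9.1.2 whether 5.75 and 4.90 are unadjusted or baseline-adjusted. If unadjusted, use t; if adjusted, give the assumed baseline correlation.

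The cost is a text and table correction. Enrolment, design and analysis stay as they are.

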9.2. Efficacy Analysis

The primary efficacy analysis of Stage 1 and Stage 2 is based on the CDASI activity scores at Week 12. The primary efficacy analysis in Stage 3 is based on the TIS at Week 12. Analysis of efficacy endpoints will be performed for the modified intenttotreat (mITT) population, defined as all randomized participants who receive at least 1 dose of investigational product. Formal statistical testing for efficacy will be based on Stage 1 data only.

All treatment periods in this study will be conducted in a double blinded fashion. During this period, the participants, investigators and sponsor (or designee) will be blinded to randomized study treatments. After the treatment period is completed for all the participants, some members of the study team will be unblinded so that a report for the corresponding data can be generated. The participants, investigators, and individuals from the sponsor (or designee) who interact with the investigators and monitor safety will continue to be blinded to individual study treatments throughout the follow up period of the study. The official database release will occur after the last participant completes the last visit. The Clinical Study Report (CSR) will be based on the data generated following the database release.

9.2.1. Analysis of the Primary Endpoint

9.2.1.1. Analysis of Primary Endpoint in Stage 1

The treatment effect is defined as the difference (mean change from baseline at Week 12 in the active treatment group minus the mean change from baseline at Week 12 in the placebo group) in the mean change of CDASI activity score from baseline at Week 12.

The estimates for treatment effect will be obtained by fitting the longitudinal analysis of covariance (LANCOVA) model to the CDASI activity score change from baseline. The model will include treatment (active dose and placebo), week and treatment by week interaction as fixed effects and baseline value as a covariate. An unstructured variance-covariance matrix will be allowed.

A sensitivity analysis will be based on the analysis of covariance (ANCOVA). The ANCOVA-based estimation of the treatment effect will use the observations collected at baseline and Week 12 visits only and will eliminate the complexity of modeling the covariance between the repeated measures of outcome observed at different visits. The resulting estimate may be slightly less precise than the LANCOVA-based estimate.

Estimates and the confidence intervals for treatment effect will be presented for each of these methods.

9.2.1.2. Analysis of Primary Endpoint in Stage 2

The treatment effect is defined as the difference (between each active treatment group and placebo group across the two stages) in the mean change of CDASI activity score from baseline at Week 12. Baseline is defined as Day 1.

Estimates and 90% CI will be computed. No p-values will be computed for the analysis in this stage.

The estimates will be obtained using the same LANCOVA model as described in Section 9.2.2.1.

Data permitting, the secondary analysis for the primary endpoint in Stage 2 will be the PF-06823859 exposure-response analysis of the combined data from Stage 1 and Stage 2. The Population Modeling Analysis Plan, (PMAP) will describe the evaluation of the relationship between PF-06823859 exposures and response at Week 12. Analyses developed to characterize this exposure-response relationship will not be part of the Clinical Study Report (CSR) and may be reported separately.

Additional sensitivity analysis will be described in the SAP.

9.2.1.3. Analysis of Primary Endpoint in Stage 3

The primary objective in Stage 3 is to determine the safety and tolerability of PF-06823859 in adult DM participants with moderate muscle disease. No efficacy analyses will be performed for the primary endpoint. All safety data will be reported according to sponsor standards consistent with the previous stages.

9.2.2. Analysis of Secondary Endpoints

9.2.2.1. Analysis of the Secondary Endpoints in Stage 1

The values of CDASI activity and damage scores at each visit will be summarized by descriptive statistics. The estimates for treatment effect will be obtained by LANCOVA and ANCOVA methods described in Section 9.2.1 where the change from baseline of a corresponding score (ie, activity or damage score) will be used as a dependent variable. The ANCOVA analysis will be used as supportive analysis. Estimates and the confidence intervals for treatment effect will be presented for each of these methods.

9.2.2.2. Analysis of the Secondary Endpoints in Stage 2

The analyses and summaries of the secondary endpoints in Stage 2 will be the same as those in Section 9.2.2.1 except that they will be conducted for the data across the two Stages. No p-values will be presented for these analyses.

As a supportive analysis, summaries will also be presented for change from baseline in CDASI activity score after 12 weeks of active treatment, which includes pooled data from participants who received active treatment from Day 1 to Week 12 (CDASI measured at Week 12) and participants who received active treatment from Week 12 to Week 24 (CDASI measured at Week 24). This may be compared to the participants receiving placebo during the first 12 weeks. Baseline is defined as Day 1 for participants who received active treatment from Day 1 to Week 12 for participants who received active treatment from Day 1 to Week 12. Baseline is defined as Week 12 for participants who received active treatment from Week 12 to Week 12 to Week 12 to Week 24. Further details will be provided in the SAP.

9.2.2.3. Analysis of the Secondary Endpoints in Stage 3

The TIS at baseline is 0 indicating no change. The TIS at post baseline visits is scored as relative change from baseline. The absolute value of the TIS at each post baseline visit will be summarized by descriptive statistics. The estimates of the treatment effect from Baseline to Week 12 will be obtained by LANCOVA where the TIS will be used as a dependent variable. The model will include treatment (active dose and placebo), week and treatment by week interaction as fixed effects. An unstructured variance-covariance matrix will be allowed.

Estimates and the 90% confidence intervals for treatment effect will be presented. No p-values will be presented for these analyses.

As a supportive analysis, the mean TIS after receiving 12 weeks of active treatment will also be estimated among all participants who completed or had the chance to complete the fixed sequence using pooled data from participants who received active treatment from Day 1 to Week 12 (TIS measured at Week 12) and participants who received active treatment from Week 12 to Week 24 (TIS measured at Week 24). This may be compared to the placebo during the first 12 weeks. Baseline is defined as Day 1 for participants who received active treatment from Day 1 to Week 12. Baseline is defined as Week 12 for participants who received active treatment from Week 12 to Week 24. Further details will be provided in the SAP.

The CSM of the TIS, including PGA, PtGA, MMT, HAQ-DI, muscle enzymes, and extra-muscular activity, at each visit will also be summarized by descriptive statistics on the absolute scale and change from baseline.

Additionally, the absolute values and change from baseline of CDASI activity and CDASI damage scores at all scheduled time points will be summarized by descriptive statistics per Section 9.2.2.1.

Further details will be provided in the SAP.

